4.1 Inclusion criteria

- Women aged over 18 years.
- Completed primary treatment for endometrial cancer within the past 36 months.
- No evidence of recurrence.
- Able to provide informed consent.
- Sufficient English language skills to participate in the group sessions.

4.2 Exclusion criteria

- Second active primary malignancy.
- Significant comorbidity that would prevent participation.
- Inability to access or use the online course platform.

5 Study Schedule

5.1 Schedule of procedures

SPONSOR REFERENCE: 1097

OurPERSPECTIVE endometrial cancer survivorship Study

Protocol Version v1.0 14/10/2025

IRAS: 363748

Procedures						
	Screening	Baseline	Week 4	Week 8-10	3-months	6-months
Visit window	± 4 weeks	± 4 weeks	± 8 weeks	± 12 weeks	± 24 weeks	± 36 weeks
Visit details	Face to face or Remote	Face to face or Remote	Remote	Remote	Remote	Remote
Invitation and expression of interest	X					
Telephone screening	X					
Informed consent	X					
Eligibility Assessment	X					
Demographics		X				
Medical history		X				
Questionnaires		X	X		X	X
Interview			X (For select participants only)	X		

SPONSOR REFERENCE: 1097

OurPERSPECTIVE endometrial cancer survivorship Study

Protocol Version v1.0 14/10/2025

IRAS: 363748

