Protocol Version v1.0 14/10/2025

IRAS: 363748

Objectives	Outcome Measures/Endpoints	Timepoint(s) of evaluation of this outcome measure
	
qualitative feedback from focus groups).
 
 – Questionnaire completion rates and data quality, to assess the practicality of collecting patient-reported outcomes in this population. – Changes in patient-reported outcomes over the course of the study, including quality of life, wellbeing, and fear of recurrence, measured using validated questionnaires (e.g. SF-36, HADS, EQ-5D-5L). – Participant preferences regarding delivery mode (virtual group versus other formats) and suggestions for improvement. – Qualitative feedback on barriers and facilitators to participation, acceptability of study materials, and relevance of course content. – Assessing how equity characteristics (PROGRESS-Plus) determine engagement and usability of the intervention. 
These outcomes will provide information on which measures are most suitable and acceptable for inclusion in the future definitive RCT.
	6-months and 12-months post-intervention.
Exploratory Objective(s) Outcome(s), Timepoint(s)		
N/A	N/A	N/A

3 Study Design

This is a single-centre feasibility study based at the University Hospitals of Leicester NHS Trust. The study will recruit women who have recently completed treatment for endometrial cancer through NHS secondary care at University Hospitals of Leicester NHS Trust. The intervention, OurPERSPECTIVE, is delivered virtually as an online group course facilitated by a gynaecology nurse specialist: the structure of the module will follow the example showed in figure 2. The content of each module is summarised in figure 3. The online course will be complemented with an interactive workbook which will be supplied to participants.

All study activities (identification, recruitment, consent, delivery of the intervention, and follow-up) will be managed through this single NHS hospital site. No other types of sites (e.g. GP practices or community venues) are involved. There are no participant identification centres; recruitment will be undertaken directly by the clinical care team at Leicester Cancer Centre.

Figure 2: Structure of a module within the OurPERSPECTIVE Course.

Figure 3: Topics for discussion in the OurPERSPECTIVE Modules.

4 Participant Eligibility Criteria

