5.4 Study assessments

Demographic and Clinical Data

Demographic information (age, sex, ethnicity, postcode) and relevant clinical details (date of completion of primary treatment, cancer and stage, and current disease status) will be obtained from routine NHS clinical records at the University Hospitals of Leicester NHS Trust. Specifically, the following information will be sought:

Anthropometric Data: Height and weight will be measured and used to calculate Body Mass Index (BMI).

SPONSOR REFERENCE: 1097

OurPERSPECTIVE endometrial cancer survivorship Study

Protocol Version v1.0 14/10/2025

IRAS: 363748

Endometrial Cancer Data: Information will be collected on recurrence, definitive treatment undertaken, menopause status.

Medical History Data: Information on other medical conditions/medications will be collected, as well as smoking and alcohol intake questions.

Equity characteristics (modified PROGRESS-Plus): Information on equity characteristics and social circumstance will be collected, with the option of 'prefer not to say' provided for information deemed to be of a sensitive nature.

Baseline Questionnaires (Week 0)

At enrolment, participants will complete self-reported questionnaires delivered electronically or on paper (depending on participant preference). These will include:

- Quality of life: SF-36
- Psychological wellbeing: Hospital Anxiety and Depression Scale (HADS)
- Multi-dimensional health-related quality of life assessment: EQ-5D-5L
- Acceptability and usability questions tailored to the intervention

Midpoint Interview (Week 4)

At week 4, selected participants will be invited to take part in a short telephone interview to assess the feasibility and acceptability during the intervention. This will be with the research fellow. The interview will be recorded using Microsoft Teams.

Post-Intervention Questionnaires (3 months)

After completing the OurPERSPECTIVE course, participants will be asked to complete the same set of questionnaires as at baseline to assess feasibility of data collection and exploratory changes in quality of life, psychological wellbeing, and fear of recurrence. It is anticipated that this data collection will be approximately 3-months since recruitment. Additional acceptability and usability questions will capture participant feedback on the intervention as a whole. Further follow up questionnaires will be sent at the 6-month and 12-month point, respectively.

OurPERSPECTIVE Course Attendance

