5.4.1 Long term follow-up assessments

This is a feasibility study and long-term follow-up beyond the 8-week intervention period includes the 3-month, 6-month and 12-month questionnaires to investigate the longer-term impact of the course.

Frequency and duration of follow-up

Participants will be sent questionnaires approximately 2 weeks after completion of the 8-week OurPERSPECTIVE course (3 month); and will be invited to participate in focus group or interviews to approximately 4 weeks after completing of intervention completion. Further long-term follow up will be completed at 6-month and 12-month of intervention completion with the included questionnaires to compare to baseline symptom burden.

Assessments

Post-intervention assessments will include the same questionnaires completed at baseline (SF-36, HADS, EQ-5D-5L, acceptability/usability questions) and an optional focus group.

SPONSOR REFERENCE: 1097

OurPERSPECTIVE endometrial cancer survivorship Study

Protocol Version v1.0 14/10/2025

IRAS: 363748

These measures will capture short-term changes in wellbeing and evaluate the acceptability of the intervention.

Differences from standard care

The course and the assessments are additional to standard NHS follow-up, which typically focuses on clinical surveillance for recurrence and does not include a structured survivorship course, questionnaires or peer-support evaluation.

Retention strategies

Retention will be supported through flexible scheduling of questionnaires (online or postal completion), reminder emails/telephone calls, and provision of modest shopping vouchers as a token of thanks. The focus on short-term follow-up reduces risk of attrition.

Identification of lost to follow-up

Participants will be considered lost to follow-up if they do not return post-intervention questionnaires and cannot be contacted after three attempts (e.g. email, phone, postal reminder).

Handling missed data

If questionnaire time-points are missed, participants will still be invited to complete subsequent assessments where possible. Early-exit data will be recorded if participants withdraw before completing the study.

Data from non-adherers

For participants who discontinue the intervention but do not withdraw consent, available outcome data (e.g. questionnaires completed up to that point) will still be retained and included in feasibility analysis.

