8.3.3 Secondary outcome analysis

Secondary outcomes will assess change in participant-reported quality of life and psychological well-being. Data will be collected using the SF-36, Hospital Anxiety and Depression Scale (HADS), and EQ-5D-5L at baseline, post-intervention, and 3-, 6- and 12-month follow-ups. Descriptive statistics will summarise scores at each timepoint. Mean within-participant changes from baseline will be presented with 95 % confidence intervals and standardised effect estimates.

Qualitative data from midpoint interviews (week 4) and the post-intervention focus groups/interviews will also be analysed using Reflexive Thematic Analysis.

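### The visit windows in section 5.1 are wider than the gaps between visits and conflict with the follow-up times given elsewhere in the protocol

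*Protocol*

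**What the plan says.** The schedule in section 5.1 has six columns, "Screening Baseline Week 4 Week 8-10 3-months 6-months", and under them the row "Visit window ± 4 weeks ± 4 weeks ± 8 weeks ± 12 weeks ± 24 weeks ± 36 weeks". There is no 12-month column. The questionnaire row, "Questionnaires X X X X", marks baseline, week 4, 3 months and 6 months, and leaves week 8-10 blank.

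The timings elsewhere are:

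- **Baseline.** Section 5.4 puts it at enrolment, under "Baseline Questionnaires (Week 0"; section 2 puts it before the trial begins.
- **3 months.** Section 5.4 says "It is anticipated that this data collection will be approximately 3-months since recruitment". Section 5.4.1 says "Participants will be sent questionnaires approximately 2 weeks after completion of the 8-week OurPERSPECTIVE course (3 month". Section 2 counts 3 months from the end of the intervention.
- **6 and 12 months.** Sections 2 and 5.4.1 count both from the end of the intervention.

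Section 8.3.3 analyses the scores at baseline, post-intervention, 3, 6 and 12 months: "Mean within-participant changes from baseline will be presented with 95 % confidence intervals and standardised effect estimates". The protocol gives no rule for assigning a form to a timepoint when windows overlap.

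**The concern.** A visit window should let a reader tell one timepoint from the next. Here the tolerance at 3 months is 24 weeks either side and at 6 months 36 weeks either side, in a study whose whole follow-up is 12 months. Windows this wide exclude almost nothing.

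The change scores of section 8.3.3 are the study's only quantitative estimates of change, and each is labelled by timepoint. If a form well past the next scheduled point still counts as on time, the label no longer says how long after the course the score was taken. If a baseline form can be completed once sessions have started, the reference value may already reflect some exposure. No later analysis rule can restore a baseline taken before the course.

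**Working it through.** **Inputs.** Half-widths from section 5.1: baseline 4, week 4 8, week 8-10 12, 3 months 24, 6 months 36 weeks. Week 0 is baseline (section 5.4). The course lasts 6 to 8 weeks (section 5.5.1). One month is 365.25/12/7 = 4.35 weeks, so 3, 6 and 12 months are about 13, 26 and 52 weeks.

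**Step 1: windows.** Window = target week ± half-width. Baseline is 0 ± 4 = -4 to 4. Week 4 is 4 ± 8 = -4 to 12. Week 8-10 runs from 8 - 12 = -4 to 10 + 12 = 22. The later windows depend on the anchor (rounded to whole weeks):

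| Anchor | 3-month target and window | 6-month target and window | Shared weeks | 12-month target |
|---|---|---|---|---|
| Months from baseline | 13: -11 to 37 | 26: -10 to 62 | -10 to 37 | 52 |
| Months after an 8-week course | 21: -3 to 45 | 34: -2 to 70 | -2 to 45 | 60 |
| Months after a 6-week course | 19: -5 to 43 | 32: -4 to 68 | -4 to 43 | 58 |
| 3 months = 2 weeks after an 8-week course; 6 and 12 months after the course | 10: -14 to 34 | 34: -2 to 70 | -2 to 34 | 60 |

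In every row both windows open before week 0 and the 12-month target lies inside the 6-month window. The overlap covers about 47 of the 48 weeks of the 3-month window in the first three rows, and 36 of 48 in the last.

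**Step 2: compare with the gaps.** Two symmetric windows stay apart only if their half-widths add up to no more than the gap between the targets.

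- Baseline to week 4: 4 + 8 = 12 weeks, against a gap of 4.
- Week 4 to 3 months: 8 + 24 = 32, against 6 to 17 depending on anchor (10 - 4 to 21 - 4).
- 3 to 6 months: 24 + 36 = 60, against 13 to 24 (26 - 13 to 34 - 10).
- 6 to 12 months: 36 for the 6-month window alone, against 26.

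Every adjacent pair fails, under every anchor.

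**Step 3: what late returns are allowed.**

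- Baseline: up to week 4. If enrolment coincides with session 1, weekly sessions at weeks 0, 1, 2 and 3 come first, which is four of eight.
- 3 months: up to 37 - 26 = 11 weeks past the 6-month point counting from baseline, and 45 - 34 = 11 weeks counting from course end. Under the two-weeks-after-course meaning, the window closes at week 34, about at the 6-month point and not beyond it.
- 6 months: up to 62 - 52 = 10 weeks past the 12-month point, or 70 - 60 = 10 weeks.

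**Step 4: the 3-month target itself.** The three meanings put it at about week 13, 10 or 21, a spread of 11 weeks before any window is applied. Section 8.3.3 also lists a post-intervention score separately from the 3-month one, whereas section 5.4.1 treats the form sent about 2 weeks after the course as the 3-month form, and section 5.1 has no questionnaire at week 8-10.

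**The case against.** The strongest reply is that forms are issued by timepoint. Baseline is taken at enrolment, the 3-month set follows the course, and the 6- and 12-month sets are sent at those points. A form cannot come back before it is sent. This stands, and it removes most of the early side of the windows. A reader of section 5.1 alone might infer that one questionnaire could count as baseline, week 4, 3-month or 6-month, or that change scores have no defined time at all. Sections 2, 5.4 and 5.4.1 do not support that: nominal times exist, although the 3-month one is contradictory.

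A reader might also infer that questionnaire completion will be inflated. The outcome is worded "Questionnaire completion rates and data quality, to assess the practicality of collecting patient-reported outcomes in this population", and nothing ties it to the windows. Section 5.4.1 defines loss to follow-up by non-return and three failed contact attempts. Nor is finding the best follow-up timing for the later trial a stated aim; section 2 speaks of which measures are suitable and acceptable.

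Three further replies carry less weight. The figures may have been meant as elapsed weeks or latest dates, but they are printed with ± and no other reading is given; if so, the row is still wrong. A statistical analysis plan could set analysis windows, but this row governs conduct. The study is small and descriptive, which lowers the severity without making the row workable.

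**Conclusion.** The point holds as a conflict within the protocol. The overlap of the windows does not depend on the choice of anchor. The 3- and 6-month windows share 36 to 47 weeks, and the 6-month window always contains the 12-month target.

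The practical harm lies on the late side. A 6-month form up to 10 weeks past 12 months is in window. So is a 3-month form up to 11 weeks past 6 months, under two of the three meanings of the 3-month point. That a late baseline form may follow part of the course rests on an assumption that enrolment is close to session 1: section 5.4 sets week 0 at enrolment, the course runs in cohorts of about 10, and the gap between the two is not stated.

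Severity is should-fix. About 30 women are planned, no hypothesis is tested, and recruitment and course completion do not use these windows. What is affected is the meaning of the timepoint labels in section 8.3.3.

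**What to change.** - Replace the window row in section 5.1 with non-overlapping windows tied to one stated anchor. Widths such as ±2 weeks at 3 months and ±4 weeks at 6 and 12 months are examples only; the documents do not determine them.
- Require the baseline questionnaire to be completed before session 1.
- Choose one meaning for the 3-month point, use it in sections 2, 5.1, 5.4 and 5.4.1, and state how it relates to the post-intervention timepoint in section 8.3.3.
- Add a 12-month column to section 5.1.
- Record the actual completion date of every form. Keep late returns and flag them as out of window.

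The cost is a protocol edit somewhat larger than one table row, with no change to sample size or to the assessments themselves. The downside is that some returns will be reported as late.

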5.2 Recruitment

The recruitment phase will commence as soon as all necessary approvals have been received. Potential participants will be identified and/or contacted through the approaches described below. In all instances participants will be provided with a copy of the Participant Information Sheet, confidentiality and privacy notice, and invitation letter.

5.2.2 Screening and eligibility assessment

Telephone pre-screening

Following a potential participant's expression of interest, a pre-screening telephone call will be arranged to provide further information about the study and to check their suitability to take part.

A pre-screening eligibility check will be conducted to confirm the following criteria:

- Age ≥ 18 years
- Completed primary treatment for endometrial cancer within the past 36 months
- No evidence of recurrence (as recorded at most recent clinical follow-up)
- Ability to provide informed consent

SPONSOR REFERENCE: 1097

OurPERSPECTIVE endometrial cancer survivorship Study

Protocol Version v1.0 14/10/2025

IRAS: 363748

- Access to and ability to use an online platform for group sessions
- Sufficient English language skills to participate in the course

Where pre-screening eligibility is confirmed, the participant will be invited to proceed to full enrolment and baseline data collection.

Baseline screening / enrolment

There are no additional medical tests or procedures required beyond routine clinical care. Baseline eligibility confirmation will include:

- Review of recent clinic records by the direct care team to confirm no evidence of recurrence
- Confirmation of treatment completion date (within the past 36 months)
- Confirmation of that participant is able to attend the online course

Participants who meet all criteria will then provide written or electronic informed consent and be enrolled in the study.

5.2.3 Informed consent

Following the provision of the Participant Information Sheet, the potential participant will be given as much time as they need and at least 24 hours to decide whether or not they would like to take part.

The process of obtaining informed consent will include a discussion between the potential participant and a member of the research team, which will detail no less than: the exact nature of the study, the implications and requirements of the protocol, and any potential risks involved in taking part. It will be clearly explained that participation is voluntary and that the participant is free to withdraw from the study at any time, without giving a reason, without prejudice to their future care, and without their legal rights being affected. They will also be reminded that any data collected up to the point of withdrawal will be retained.

Potential participants will be given the opportunity to ask questions about taking part and withdrawing, and will have these answered before signing consent.

The person who obtains consent will be suitably qualified and experienced, and will have been authorised to do so by the Principal Investigator as detailed on the Delegation of Authority and Signature Log for the study.

All participants will be required to give written informed consent prior to any study activities taking place.

SPONSOR REFERENCE: 1097

OurPERSPECTIVE endometrial cancer survivorship Study

Protocol Version v1.0 14/10/2025

IRAS: 363748

In-person consent

Written consent will be obtained by means of a participant's dated signature and the dated signature of the person who presents and obtains consent, using the latest approved version of the informed consent form. The original signed form will be retained within the Investigator Site File (ISF). A copy will be given to the participant, and another copy placed in the participant's NHS medical notes.

Remote consent

Where participants prefer, consent may also be obtained remotely. In such cases, the Participant Information Sheet and consent form will be sent electronically or by post in advance. The research team will arrange a remote consent discussion (telephone or video call) to review the information, answer questions, and confirm understanding. Participants will sign the consent form either electronically (via secure e-consent system) or by printing, signing, and returning by post. The research team member taking consent will then countersign the form. A fully signed copy will be provided to the participant and another copy will be retained in the ISF.

Language requirements

The study mandates English language proficiency due to the nature of the intervention, this is stated in our inclusion criteria. As such, Participant Information Sheets and consent forms will be written in plain language English.

5.3 Randomisation

Not Applicable.

5.3.1 Blinding and code breaking

Not Applicable.

5.4 Study assessments

Demographic and Clinical Data

Demographic information (age, sex, ethnicity, postcode) and relevant clinical details (date of completion of primary treatment, cancer and stage, and current disease status) will be obtained from routine NHS clinical records at the University Hospitals of Leicester NHS Trust. Specifically, the following information will be sought:

Anthropometric Data: Height and weight will be measured and used to calculate Body Mass Index (BMI).

SPONSOR REFERENCE: 1097

OurPERSPECTIVE endometrial cancer survivorship Study

Protocol Version v1.0 14/10/2025

IRAS: 363748

Endometrial Cancer Data: Information will be collected on recurrence, definitive treatment undertaken, menopause status.

Medical History Data: Information on other medical conditions/medications will be collected, as well as smoking and alcohol intake questions.

Equity characteristics (modified PROGRESS-Plus): Information on equity characteristics and social circumstance will be collected, with the option of 'prefer not to say' provided for information deemed to be of a sensitive nature.

Baseline Questionnaires (Week 0)

At enrolment, participants will complete self-reported questionnaires delivered electronically or on paper (depending on participant preference). These will include:

- Quality of life: SF-36
- Psychological wellbeing: Hospital Anxiety and Depression Scale (HADS)
- Multi-dimensional health-related quality of life assessment: EQ-5D-5L
- Acceptability and usability questions tailored to the intervention

Midpoint Interview (Week 4)

At week 4, selected participants will be invited to take part in a short telephone interview to assess the feasibility and acceptability during the intervention. This will be with the research fellow. The interview will be recorded using Microsoft Teams.

Post-Intervention Questionnaires (3 months)

After completing the OurPERSPECTIVE course, participants will be asked to complete the same set of questionnaires as at baseline to assess feasibility of data collection and exploratory changes in quality of life, psychological wellbeing, and fear of recurrence. It is anticipated that this data collection will be approximately 3-months since recruitment. Additional acceptability and usability questions will capture participant feedback on the intervention as a whole. Further follow up questionnaires will be sent at the 6-month and 12-month point, respectively.

OurPERSPECTIVE Course Attendance

Attendance at each of the 8 weekly online group sessions will be recorded in the case report form. Sessions will last approximately 60 minutes and will be facilitated by a gynaecology nurse specialist. Group rules will be set at the start, and each session will end with a short debrief, and mood self-rating in the accompanying guided workbook provided to patients. Participants will be given a workbook to support their attendance on the course and a separate reflective diary where they can document their thoughts, experiences and feedback of the different modules. The diary will be returned to the research team at the end of the course; however, the participants will be able to keep the course workbook.

SPONSOR REFERENCE: 1097

OurPERSPECTIVE endometrial cancer survivorship Study

Protocol Version v1.0 14/10/2025

IRAS: 363748

Focus Group

Within 4 weeks of course completion, participants will be invited to take part in a virtual focus group to provide qualitative feedback on their experience, the data collection from each participant will conclude at 3-months. Discussions will explore perceived benefits, challenges, and suggestions for improvement. Sessions will be audio recorded, transcribed, and anonymised for analysis. The number of participants in each focus group will be 4-6 in order give participants time and opportunity to share their experiences. For individuals who do not wish to discuss their experiences openly, the option of a one-one virtual or telephone interview with the research fellow will be offered.

Withdrawal or Early Exit

If a participant withdraws before completing the course, the reason (if provided) will be recorded. Participants will be asked if they are willing to complete an early-exit telephone interview in order to explore their reasons and what could be done to improve the course to reduce future withdrawals.

Mode of Delivery

All questionnaires will be completed remotely (online or postal). The OurPERSPECTIVE intervention and focus groups will be delivered virtually (videoconferencing platform). No face-to-face study visits are required.

